4.2.6 Proteinuria 2+ or greater by urine dipstick

4.2.7 Signs or symptoms suggestive of acute HIV infection

4.2.8 Any other reason or condition that in the opinion of the investigator would interfere with participation, complicate interpretation of study outcome data, or otherwise interfere with achieving the study objectives.

4.3 Enrollment Procedures

4.3.1 Prior to implementation of this protocol, sites must have the protocol and consent form approved by their local institution review board (IRB). Sites must be registered with and approved by the CCTG Data Center. Site registration must occur before any subjects can be enrolled in this study.

4.3.2 Once a candidate for study entry has been identified, details will be carefully discussed with the subject. The subject will be asked to read and sign the consent form that was approved by both the local IRB and the CCTG Data Center.

4.3.3 A patient identification number (PID) will be assigned to each patient screened for the study. PIDs will include site code and be formatted to be compatible with the BIT data core. PIDs will not be reassigned even if the subject fails to enter the study. The PID must be included on every CRF and subject specimen during the study. Each site must maintain a master list of PIDs in a central location. The patient registration and inclusion/exclusion CRF must be completed on the online system.

5.0 STUDY TREATMENT

5.1 Regimens, Administration, and Duration

5.1.1 Regimens

Subjects will be randomized 1:1 to one of the two treatment arms:

ARM A: FTC/TDF 200/300 mg fixed dose combination once daily + iTAB

ARM B: FTC/TDF 200/300 mg fixed dose combination once daily

- ♦ Use of the FTC/TDF fixed dose combination is not allowed if the CrCl is <50 mL/min, which should be confirmed within 7 days. TDF/ FTC should be discontinued if confirmed.

5.1.2 Administering and Dispensing

Emtricitabine/tenofovir disoproxil fumarate fixed-dose combination containing 200 mg of emtricitabine and 300 mg tenofovir disoproxil fumarate will be administered orally as one tablet once daily with or without food.

Enough study product should be dispensed to last until the subject's next scheduled visit.

5.1.3 Duration

Subjects will participate in this study until 48 weeks beyond the enrollment of the last subject with a maximum duration of 96 weeks for any subject. Subjects may receive study treatment until their last study visit.

Subjects will receive study treatment for the duration of the study unless they meet criteria for discontinuation.

5.2 Study Product Formulation

Emtricitabine/tenofovir disoproxil fumarate (FTC/TDF, Truvada®): 200 mg/300 mg coformulated tablet. Store at 25°C (77°F); excursions permitted to 15°-30°C (59°-86°F) [see USP Controlled Room Temperature].

5.3 Pharmacy: Product Supply, Distribution, and Accountability

5.3.1 Study Product Supply/Distribution

Emtricitabine/tenofovir disoproxil fumarate will be supplied by Gilead Sciences through the UCSD/AVRC Research Pharmacy and distributed to all sites.

The site pharmacist can obtain study product for this protocol by following the instructions in the CCTG-595 Pharmacy Manual.

5.3.2 Study Product Accountability

The site pharmacist is required to maintain complete records of all study product received from the UCSD /AVRC Research Pharmacy. All unused study product must be returned to the sponsor (or as otherwise directed by the sponsor) after the study is completed or terminated. The procedures to be followed are provided in the CCTG-595 Pharmacy Manual.

5.4 Concomitant Medications

Whenever a concomitant medication or study agent is initiated or a dose changed, site investigators must review the concomitant medications and study agent's most recent package inserts, Investigator's Brochures to obtain the most current information on drug interactions, contraindications, and precautions.

5.4.1 Prohibited Medications (Refer to Section 4.2 for addition information on prohibited medications).

5.4.1.1 All investigational drugs

5.4.1.2 All HIV vaccines

5.4.1.3 Any immunomodulators

5.4.1.4 Systemic cytotoxic chemotherapy

5.4.1.5 All other antiretroviral medications (excluding FTC/TDF given as PEP or PrEP)

5.4.1.6 Drugs with known nephrotoxicity

Subjects must have discontinued prohibited medications at least 30 days prior to entry.

5.5 Adherence Assessment

Throughout the study, the documentation of adherence to study drug is essential. The adherence questionnaire will be completed during each study visit. This will include the ACTG 4-day adherence questionnaire as well as the VAS over the previous 4 week period, except for the week 4 visit where adherence will be assessed since starting medication.

6.0 CLINICAL AND LABORATORY EVALUATION

6.1 Schedule of Evaluation

Schedule of Evaluations	Screen	Study Weeks of Follow-up								Suspected HIV/STI infection ⁴	Interim for Missed Visit ⁵
	Within 30 days	0	4	12	24 or 72	36 or 60 or 84	48 or 96	End of Study or premature D/C	Post-study, 3-month		
Visit Window		± 14 days									
Informed Consent	X										
Medical/Medication History	X										
Documentation of HIV status by rapid HIV test plus NAT or Ag/Ab combo assay	X										
Randomization		X									
Pre/Post Assessments ¹		X						X			
iPAD self-administered survey ²		X	X	X	X	X	X	X		X	X
Risk reduction Counseling		X	X	X	X	X	X	X		X	X
Review PrEP adherence (ACTG 4 day and VAS)			X	X	X	X	X	X		X	X
Clinical Hx of STI and PREP use		X	X	X	X	X	X	X		X	X
Assessment of adverse events		X	X	X	X	X	X	X		X	X
Targeted exam (as clinically indicated)	X	X	X	X	X	X	X	X		X	X
Concomitant medications		X	X	X	X	X	X	X		X	X
Dispense TDF/FTC (if HIV rapid test negative)		X	X	X	X	X	X				X
Calcium and vitamin D intake						X ⁶					
Phone call follow-up									X		

Schedule of Evaluations	Screen	Study Weeks of Follow-up							Post-study, 3-month	Suspected HIV/STI infection ⁴	Interim for Missed Visit ⁵
	Within 30 days	0	4	12	24 or 72	36 or 60 or 84	48 or 96	End of Study or premature D/C			
Laboratory											
CBC/Chemistry	X										
Calculated GFR (serum Cr)	X		X	X	X	X	X	X			X
Urine Dipstick	X		X	X	X	X	X	X			X
Rapid HIV Test		X	X	X	X	X	X	X		X	X
STI testing- throat, rectum, urine; blood RPR		X			X		X	X		X	X
Rectal swab (x2)		X			X ⁷		X ⁷				
HBsAg-/HBsAB-/HBcAB	X										
If HBsAg-/HBsAB-/HBcAb+, Hepatitis B DNA PCR	X										
HIV RNA, CD4, HIV genotype, banked PBMC		X ³	X ³	X ³	X ³	X ³	X ³	X ³		X ³	X ³
Plasma banked specimen		X	X	X	X	X	X	X		X ³	X
Banked clotted blood		X									
Dried blood spot				X	X	X	X	X		X ³	X
Urine for storage		X	X	X	X	X	X	X		X	X
¹ Pre: attitudes toward safe sex, disclosure, access to care, social support, texting ability, Kalichman sexual compulsivity; Post: satisfaction with iTAB; Pre/Post: HIV literacy, stigma and disclosure, AUDIT, DAST-10 ² includes: risk behavior, adherence assessments, intention to adhere, PHQ9, SCID substance use screen ³ Perform if HIV+ ⁴ Any time history or symptoms suggest potential HIV or STI, check with study MD for appropriate test ⁵ Subjects may have an interim visit if past window of scheduled visit, next visit should be back to regular schedule ⁶ To be performed at week 36 only ⁷ Performed only once on or after Week 48 coinciding with STI screening (Week 48, 72, or 96)											

6.2 Definitions for Schedule of Events and Timing of Evaluations

6.2.1 Screening Assessments

Occur prior to the subject taking any study medications, treatments, or interventions

Patient Registration: A patient identification number (PID) will be assigned to each patient screened for the study. PIDs should not be reassigned even if the patient fails to enter the study. The PID must be included on every CRF and patient blood sample. Each site must maintain a master list of PIDs in a central location. The patient registration and inclusion/exclusion CRF must be completed on the online system.

All subjects interested in screening for the PrEP project will sign an informed consent document that had been approved by local IRB at the site. Screening procedures (see schedule of evaluations) will include: determination of inclusion and exclusion criteria; confirmation of HIV status and screen for acute HIV symptoms. HIV serology will be performed as part of screening, including rapid HIV test and NAT or equivalent (antigen antibody test). Laboratory screening will include CBC, chemistry values, GFR (Cockcroft-Galt) LFT and HBsAg. If a subject qualifies and signs consent the window to complete the baseline assessment and start PrEP will be two weeks.

6.2.2 Entry Evaluations (day 0)

Randomization: subjects that meet all the inclusion and exclusion criteria will be randomized at their day 0 entry visit. Subjects will be randomized to receive standard of care or the iTAB adherence intervention, stratified by site. Subjects randomized to the iTAB intervention will set up the customized text message stems and enter the timing of the text message reminders; the information will be entered in the online iTAB system by the study coordinator.

At baseline all subjects will receive HIV transmission risk reduction counseling by a health educator and detailed information about the use of PrEP, including the risks, potential adverse events and the critical importance of drug adherence.

6.2.3 On-Study Evaluations

After counseling, laboratory testing and randomization, participants will receive sufficient TDF/FTC study medication to last until the next scheduled visit (either 4 or 12 weeks) through the investigational pharmacy. Medication renewals will not be available if a subject misses a scheduled appointment. An informational pamphlet on TDF/FTC will be provided that will summarize the label package insert information for patients (in English or Spanish) with changes made to tailor the information for someone that is not HIV infected. Participants will be directed to take one pill once a day at a convenient routine time. If there are missed doses, participants will be told to take the next scheduled dose on time and not to take any additional pills to catch up. Bottles with any remaining missed doses will be returned to the pharmacy at the time of medication renewal and the number of untaken doses will be recorded. At each clinic visit, TDF/FTC medication adherence will be

reviewed by the clinician, adverse events will be queried and adherence and barriers to adherence will be discussed. All subjects will receive episodic adherence counseling within the confines of routine clinic visit. Each clinic visit will also include blood draw for calculated GFR (serum creatinine) and plasma FTC drug levels, and HIV testing. STI testing including NAT screening for GC and chlamydia from throat and rectal swabs and from urine and RPR from blood will be done at week 0 and every 24 weeks thereafter.

Adherence and Behavioral Assessments

We will measure adherence using the ACTG medication adherence questionnaire [25]. At each follow-up visit, the ACTG four-day questionnaire will be administered using the web-based data capture system. The instrument tracks the number of doses skipped over the past four days and reasons why medications may have been skipped. In addition, we will ask their ability to adhere by Likert scale and use the Visual Analog Scale (VAS), which appears as an ordinal scale representing the percent of medication taken relative to that which has been prescribed over the past 4 weeks. Subjects are presented with a line anchored at 0% and 100% and are asked to mark a line on the scale indicating their own PrEP adherence [26].

In the standard study visit, the coordinator will perform HIV testing and blood work, review test results, provide TDF/FTC prescriptions, discuss medication use, adherence, risk reduction and troubleshoot any barriers. The standard behavioral survey will include assessment of TDF/FTC adherence, HIV transmission risk behaviors, substance use, depression scores and other risk behavior details (e.g. sexual partnerships, sexual acts, condom use).

Laboratory Safety Assessments

At follow-up clinic visits, all participants will have a blood drawn for creatinine clearance estimates. A rapid test for HIV will be performed. HIV test results will be provided during the clinic visit. If there are grade 3-4 adverse events (thought to be related to study medication- see toxicity section) or HIV seroconversion is detected, the participant will be called to discontinue TDF/FTC and to come to the clinic as soon as feasible. Any positive rapid test will be confirmed by Western Blot and HIV RNA; CD4 cell count and an HIV genotype for drug resistance will be done. Newly diagnosed HIV subjects will be counseled and be linked to HIV clinical care within the existing clinic or to another provider

designated by the participant. All PrEP-related clinic visits, laboratory testing and TDF/FTC medication will be provided by the study without charge to the subject.

FTC Qualitative Plasma Concentration as an Adherence Marker:

Plasma will be drawn at every visit starting at week 4 for FTC concentrations. Samples will not be run in real time and will not be available for clinical use.

Chlamydia, gonorrhea and syphilis testing

Subjects will have day 0 and every 24-week assessment to include urine and swabs from the rectum and throat for NAT testing for Chlamydia and gonorrhea. Blood will be drawn for RPR. In between visits, subjects will be told to come to the study nurse if they experience symptoms of an STI. They will also be asked if they were tested elsewhere between visits. All new STI cases will be referred to their provider or the Department of Health for treatment. They will be given a card to have filled out documenting treatment given, which they will be asked to bring back to their next study visit. All new STI cases will also be counseled on the need for partner therapy and will suggest that they receive assessment and treatment or partner delivered therapy. STI testing can also occur as an interim visit for high-risk exposure or symptoms suggestive of new STI.

Sexual Risk Counseling

Standard of care HIV risk reduction counseling will be providing to all participants consistent with pre- and post-test counseling for persons receiving community HIV testing. The study will provide streamlined in-person risk reduction counseling at each visit that will use the RESPECT paradigm of focusing on a single risk behavior as identified by the subject. The goal of brief and targeted counseling is to help the individual to identify his most significant risky behavior and to implement concrete actions to decrease the specific risk behavior until the next study visit. Participants will undergo this process at each visit.

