3.0 STUDY DESIGN

3.1 Study Design

CCTG 595 is a comparative, interventional study that uses text messaging to improve adherence of PrEP in MSM and transgender that are at high risk of acquiring HIV. We will conduct an open-label, randomized, controlled clinical trial to evaluate an intervention strategy that uses a developed texting adherence method, the iTAB system, to improve adherence and retention compared to standard of care which will not have iTAB (see study schema). The RCT will occur in the context of implementation of PrEP at three large, diverse, urban HIV care clinics in the CCTG network at UCLA-Harbor, USC and UCSD and a fourth site at the Long Beach Public Health Department. These sites are collaborating with local testing sites to provide an integrated program that identifies individuals at highest risk for HIV acquisition and link them into preventive care that will provide the assessment, dispensing and monitoring of PrEP. A uniform system of HIV testing, risk assessment, health education and behavioral/adherence counseling will be developed for use at consortium sites.

Study enrollment criteria is based on the CDC guidance for PrEP use among MSM and transgender with ongoing risk for HIV infection. All subjects will be confirmed to be uninfected with no contraindication to TDF/FTC. Subjects will be randomized at baseline to iTAB versus SoC. Randomization will be stratified by CCTG site. Study visits will include screening, baseline, week 4 and 12 initial visits and then visits every 12 weeks. Visits for iTAB and SoC arms will both include routine HIV testing and counseling, STI testing, adherence counseling, and medical monitoring. Each visit will include a computer-assisted survey for self-reported adherence assessment and risk behaviors. Drug level monitoring will be performed for FTC qualitative levels in retrospect on banked samples and additional banked specimens will be available for future use and TDF measurement. Adherence by self-reported measures and FTC levels will be used for the main and secondary analyses of the study. Additional outcomes for the study will include changes in risk behavior and determinants of PrEP adherence. Outcomes will be assessed at 48 weeks and for the cumulative follow up of all participants. The study will continue for 48 weeks after randomization of the last participant (up to 96 weeks for any subject).

In order to have adequate representation of African Americans in the study population,

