8.0 CRITERIA FOR TREATMENT DISCONTINUATION

8.1 Criteria for Discontinuation from Study

- 8.1.1 Diagnosis of HIV infection.
- 8.1.2 Request by the subject to withdraw.
- 8.1.3 Request of the primary care provider if s/he thinks the study is no longer in the best interest of the subject.
- 8.1.4 Clinical reasons believed life threatening by the study physician, even if not addressed in the toxicity management of the protocol, and can no longer continue in follow up.
- 8.1.5 Subject judged by the investigator to be at significant risk of failing to

comply with the provisions of the protocol as to cause harm to self or seriously interfere with the validity of the study results.

- 8.1.6 At the discretion of the CCTG, FDA, CHRP or pharmaceutical sponsors.
- 8.1.7 Misses two consecutive scheduled visits prior to 48 weeks.
- 8.1.8 Misses one scheduled visit after 48 weeks.

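### Section 6.2.3 refuses medication renewal after a missed appointment, while the section 6.1 schedule dispenses TDF/FTC at the interim visit for a missed visit, and no passage reconciles the two

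*Combined protocol and SAP*

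**What the plan says.** **Text.** Section 6.2.3 says: "Medication renewals will not be available if a subject misses a scheduled appointment". It gives no exception. On quantity, section 5.1.2 says: "Enough study product should be dispensed to last until the subject's next scheduled visit". Section 6.2.3 agrees, with supply "to last until the next scheduled visit (either 4 or 12 weeks" away. Neither section mentions a reserve.

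**Schedule.** In the section 6.1 table, the row that begins "Dispense TDF/FTC (if HIV rapid test negative" is marked at weeks 0, 4, 12, 24/72, 36/60/84 and 48/96, and again in the last column, "Interim for Missed Visit". It is blank for screening, the end-of-study visit, the post-study call and the suspected-infection visit. Footnote 5 defines the last column: "Subjects may have an interim visit if past window of scheduled visit, next visit should be back to regular schedule". The visit window is ±14 days.

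**Spacing and withdrawal.** Section 3.1 says: "Study visits will include screening, baseline, week 4 and 12 initial visits and then visits every 12 weeks". Under 8.1.7, it takes two missed visits in a row before week 48 to meet a criterion for leaving the study. Under 8.1.8 the later criterion is: "Misses one scheduled visit after 48 weeks".

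**The concern.** The sentence and the table address the same event: a subject who did not come within the window and presents afterwards. A site that follows 6.2.3 literally sends that subject away without drug until the next regular visit. A site that follows the table dispenses, provided the rapid HIV test is negative. The blanks elsewhere in the dispensing row show that it distinguishes between visit types, so the mark in the interim column is not obviously a slip.

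Before week 48, one miss leaves the subject on study, so the conflict applies to enrolled participants, who were selected for ongoing risk of HIV (4.1.3). Their drug supply is at stake first. Second, a gap that comes from how a site reads the protocol would be scored as the participant's non-adherence in the aggregate self-report measure (9.2.2) and the percent-detectable FTC metric (9.6.3), and it could affect time to discontinuation (9.6.5).

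A smaller mismatch sits beside this. Footnote 5 and the dispensing mark have no time limit, yet after week 48 a single miss is itself a criterion for leaving the study.

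**Working it through.** The plan gives no figure on this point to reproduce. The check is a reading of the dispensing row and some arithmetic on the visit schedule.

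**Inputs.** Follow-up visits at weeks 4, 12, 24, 36 and 48, then every 12 weeks to 96 (3.1, 6.1); window ±2 weeks (6.1); supply to the next scheduled visit (5.1.2, 6.2.3). Assumption: no leftover tablets, so supply ends on the nominal date of the missed visit. Leftover tablets would shorten the gap under either reading.

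**Gap without supply.**
- Text: gap = next scheduled week − missed week, ±2 for the window at the next visit.
- Schedule: the interim visit falls after the window closes, so the gap exceeds 2 weeks. It stays below (next week − 2 − missed week) if the subject comes before the next window opens.

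| Missed visit | Text: nominal gap | With window | Schedule: gap if an interim visit is made |
|---|---|---|---|
| Week 4 | 12 − 4 = 8 weeks | 6 to 10 | more than 2, less than 6 |
| Week 12 | 24 − 12 = 12 weeks | 10 to 14 | more than 2, less than 10 |
| Week 24 | 36 − 24 = 12 weeks | 10 to 14 | more than 2, less than 10 |
| Week 36 | 48 − 36 = 12 weeks | 10 to 14 | more than 2, less than 10 |

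**48-week hypotheses.** The composite in 9.1 requires every scheduled visit to be made in window, and a missing form counts as no doses. One miss caps the score at 16/20 = 80%, below 90%. Hypothesis II needs five of five detectable FTC results, and one miss leaves at most 4 of 5. Both fail under either dispensing rule.

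**Secondary measures, worst case for one missed visit.** Take a subject who misses week 12 and presents late. Week 12 scores 0/4 under both readings. Under the text there is no supply before week 24, so week 24 is 0/4 and FTC is taken as undetectable. Under the schedule, with full adherence after the interim visit, week 24 is 4/4 and FTC is detectable.
- Self-report to week 48: 4/20 = 20 percentage points.
- FTC to week 48, counting missing samples as undetectable: 1 of 5.
- Over the nine visits to week 96: 4/36 = 11 percentage points, and 1 of 9 samples.

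In the available-data analysis of 9.6.3, the missed sample drops out of the denominator, and the same single sample counts as 1 of 4. These figures are per missed visit. Because 8.1.7 concerns consecutive misses only, a subject with two separate misses could be affected twice.

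**The case against.** **A reading that reconciles the passages.** Section 6.2 is presented as explaining the schedule. The 6.2.3 sentence can be taken to mean that drug is not refilled without a visit, with the interim visit as the make-up. The interim column supports this: it repeats the rapid HIV test, creatinine, dipstick, adverse-event check and adherence review, and the dispensing row depends on the HIV result. The table entry is also specific to missed visits, while the sentence is general. This reading is plausible and may be what was intended. It is written nowhere, however, and 6.2.3 makes no exception, so a site that applies the sentence literally is not misreading it.

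**Stronger inferences that the documents do not support.**
- *That the schedule keeps the subject on PrEP without a break.* The interim visit is optional and falls after the window, when the dispensed supply has nominally run out. It shortens the gap and does not remove it.
- *That the main result is at risk.* Both 48-week hypotheses already fail for such a subject under either rule.
- *That 20 points is an effect on the trial.* It is one subject's worst case: full adherence under one rule and no drug under the other. The documents give no rate of missed or interim visits.
- *That the comparison between arms is biased.* Randomization is stratified by site, so a site's dispensing habit should fall on both arms about equally. iTAB aims to improve retention, so missed visits may differ by arm, but that difference is part of the effect under study. A supply rule could enlarge or dilute a secondary difference; nothing in the documents shows by how much. For seroconversion, 9.6.4 itself expects few events.

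**The rule after week 48.** Footnote 5 is permissive, and a subject withdrawn under 8.1.8 has no regular schedule to return to, so the two can be read together. What stands is that the footnote carries no time limit, which is a matter of alignment.

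**Conclusion.** The inconsistency is real and the documents do not resolve it: 6.2.3 excludes renewal after a missed appointment, and the 6.1 table marks dispensing at the visit created for that case. Its direct consequence concerns drug supply to individual participants, as the gap table shows, on the assumption of no leftover tablets and with the schedule's shorter gap depending on an interim visit being made.

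The analytic consequence is limited to drug exposure and the secondary measures in 9.2.2, 9.6.3 and 9.6.5 for affected subjects. The per-visit maxima above are bounds, not expected effects, and no trial-level size can be given without the number of missed visits. The point merits a protocol clarification. It is not a threat to the primary analysis.

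**What to change.** The sponsor and investigators should reconcile section 6.2.3 with the 6.1 dispensing row and footnote 5, in one statement of whether TDF/FTC is dispensed at an interim visit. They should also align footnote 5 with 8.1.7 and 8.1.8, so that it is clear when an interim visit is possible. This review does not say which rule is right.

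Because sites may already have acted on either passage, add a descriptive table by arm of missed visits followed by no supply, placed beside the 9.2.2 and 9.6.3 results. This depends on dispensing records for each patient. Section 5.3.2 requires records of product received and refers procedures to a Pharmacy Manual that is not among the documents, so first confirm that such records exist and can be linked to missed visits.

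The cost is a short clarification to sites and, if the records allow, one descriptive table. The sample size, the primary endpoint and the planned tests stay as they are.
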